#### 10.2.3. Urinalysis

Summary statistics for each visit and change from Baseline will be presented for specific gravity and pH. Shift table will be presented for leukocytes, bilirubin, blood, glucose, ketones, protein, and urobilinogen.

## 10.3. Vital Sign Measurements

Vital signs including sitting systolic blood pressure (SBP), sitting diastolic blood pressure (DBP), body temperature, and heart rate (HR) will be recorded on the eCRF once per visit. In addition, pre-dose and hourly cardiac monitoring (blood pressures and heart rates) for hours 1-6 will be recorded for all patients at the Baseline visit. Sitting blood pressures will be recorded at each hour and in addition, standing blood pressures will be recorded at Hour 0 and Hour 6 for orthostatic changes.

Summary tables including actual values and change from Baseline (defined as pre-dose on Day 1) values will be presented for vital signs including SBP (sitting and standing), DBP (sitting and standing), temperature, and HR by treatment group for the Safety population. On Day 1, hourly changes from pre-dose in blood pressures and heart rates will be shown for all patients. For all other visits only a single timepoint will be collected and shown.

For patients requiring extended cardiac monitoring due to cardiac safety issues observed in the first 6 hours on Day 1, a listing will be provided that shows the hourly change from

pre-dose assessment through the last hour of cardiac monitoring by patient for heart rate and blood pressure.

Box plots will be provided to display the distribution of vital signs. In addition, line plots will be created to display the change from Baseline over the entire study period (not including Day 1) and separately for change from pre-dose in vital signs for the Day 1 visit.

The number and percentage of patients with SBP > 180 mmHG or < 90 mmHG and HR < 40 beats per minute will be summarized by visit for each treatment group. The number and percentage of patients with clinically relevant abnormalities will be presented by treatment group. The criteria for clinically relevant abnormalities are shown in the following table. Vital signs will be presented by patient in listings.

Vital Sign	Criteria for Abnormalities			
Temperature >38.5°C and an increase from pre-dosing of at least 1°C				
	>120 beats per minute post-Baseline, or			
Heart Rate	an increase from pre-dosing of more than 20 beats per minute, or			
Ticart Rate	<45 beats per minute post-Baseline, or			
	a decrease from pre-dosing of more than 20 beats per minute			
	>180 mmHg post-Baseline, or			
Systolic Blood Pressure	an increase from pre-dosing of more than 40 mmHg, or			
Systolic Blood I lessure	<90 mmHg post-Baseline, or			
	a decrease from pre-dosing of more than 30 mmHg			
	>105 mmHg post-Baseline, or			
Diastolic Blood Pressure	an increase from pre-dosing of more than 30 mmHg, or			
Diastone Blood Hessure	<50 mmHg post-Baseline, or			
	a decrease from pre-dosing of more than 30 mmHg			

The lowest HR observed during cardiac monitoring between hours 1-6 on Day 1 will be identified and the incidence of patients by minimum HR observed during this time period will be summarized for the following categories for each state (sitting and standing):

- ≥ 65 bpm
- 60-64 bpm
- 55-59 bpm
- 50-54 bpm
- 45-49 bpm
- 40-44 bpm
- < 40 bpm

### 10.4. Electrocardiogram

Summary tables including actual values and change from Baseline values will be presented for ECG results. The overall interpretation of the ECG results (Normal; Abnormal; not Clinically Significant; and Abnormal, Clinically Significant) will be summarized for each treatment group. ECG results will also be listed.

### 10.5. Pulmonary Function Testing

The following laboratory tests will be included for pulmonary function testing (PFT) summary tables: forced expiratory volume in 1 second (FEV1), forced vital capacity (FVC), and diffusing capacity of the lung for carbon monoxide (DLCO). For FEV1 and FVC, summary tables for actual value, change, percent change, percent predicted, change in percent predicted, and percent change in percent predicted will be produced. For DLCO summary tables for actual value, change, and percent change will be produced. DLCO is collected at the local lab for each site, so results may be collected in domestic or SI units. DLCO results in domestic units (mL/min/mmHg) will be converted to SI units (mmol/min/kPa) prior to analysis using the following conversion factor:

DLCO in SI units = (DLCO in domestic units) / 2.986

Line plots of FEV1, FVC, and DLCO results over time will be presented. All PFT results will be listed

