# 9.1.2.5. Adverse Events of Special Interest

There are a number of potential safety risks associated with RPC1063 administration that are based on the general concerns around immunosuppression (serious and opportunistic infections, malignancies), the safety findings from the Phase 1 clinical study, and the safety profile of the approved s1pr agonist fingolimod and other S1PR agonists. These include serious infections as well as the clinical consequences of its effect on the various organ systems including cardiac and

pulmonary organ systems. Other potential risks observed in the fingolimod experience, although not observed in the Phase 1 clinical trial, include hepatic, ophthalmological and dermatological effects.

Therefore, target AEs of special interest will be closely monitored in the RPC01-201 study. These AEs include infections, malignancies, cardiac (bradycardia and heart conduction abnormalities), pulmonary function (decline in FEV1, FVC, and DLCO measurements), ophthalmic (macular edema), hepatic (LFTs elevation), and dermatologic (cutaneous malignancy) abnormalities. If any abnormalities occur, they will be followed until such time as resolution is confirmed or no further improvement is expected by the investigator (based on a follow-up period of not less than 3 months). Further details on monitoring of these AEs are provided in Section 12.4.

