## Monitoring of Patients with Adverse Events of Special Interest

Several of the AEs noted in fingolimod clinical studies may be a consequence of S1P1R stimulation and will therefore be closely monitored in the RPC01-201 study. These AEs include:

- a. Bradycardia and heart conduction abnormalities. Dose-related transient, reversible bradycardia, symptomatic bradycardia, and first, second, or higher degree atrioventricular block were reported primarily as first dose effects in fingolimod studies. The heart rate reduction observed with sphingosine-1-receptor agonists is an expected effect of S1PR modulation and appears to be conducted through the same pathway as vagus nerve stimulation. In addition, these negative chronotropic effects of S1P1R agonists appear to attenuate over time secondary to S1PR desensitization and internalization on cardiac myocytes (Kovarik 2008). This effect appears to occur with increasing exposures of study drug, thus gradual titration of the dose of RPC1063 over several days may mitigate against larger reductions in HR.
- b. Pulmonary toxicity. An initial sharp decrease followed by a slow progressive decline over time in FEV1 was observed in fingolimod clinical studies. Nonclinical toxicity studies with RPC1063 have revealed the potential for pulmonary toxicity at doses considerably higher than the pharmacologically active dose. FEV1, FVC, and DLCO will be measured in all patients. Every patient whose PFTs are abnormal will be followed until such time as resolution is confirmed or no further improvement is expected by the investigator (based on a follow-up period of not less than 3 months).
- c. Hepatotoxicity. Fingolimod caused frequent, reversible liver enzyme elevations greater than 3-fold above the upper limit of normal in up to 12% of patients; this was a significant cause of cessation of therapy. In this study, clinical chemistry analyses to assess LFTs will be performed. Every patient whose LFTs are abnormal will be followed until values return to baseline.
- d. Macular edema. Instances of serious macular edema were reported in fingolimod renal transplant studies, and a 0.8% incidence was reported as an SAE in fingolimod (1.25 mg dose) MS clinical studies. Nonclinical studies with RPC1063 have not revealed eye-related toxicities. In this study, measurement of central foveal thickness by OCT will be performed in all patients. For patients

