#### **10.1.7.** Adverse Events of Special Interest

Target AEs of special interest will be closely monitored in the study. These AEs include infections, malignancies, cardiac (bradycardia and heart conduction abnormalities), pulmonary function (decline in FEV1, FVC, and DLCO measurements), ophthalmic (macular edema), hepatic (LFT elevations), and dermatological (cutaneous malignancy) abnormalities. These AEs will be summarized in tables and presented in a listing.

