### 10.2.1. Hematology

The following laboratory tests will be included in hematology summary tables of actual value and change from Baseline: red blood cell (RBC) count, total and differential WBC count (basophils, eosinophils, lymphocytes, monocytes, and neutrophils), platelet count, hemoglobin, hematocrit, mean corpuscular volume (MCV), mean corpuscular hemoglobin (MCH), and mean corpuscular hemoglobin concentration (MCHC). Total and differential WBC counts will be blinded after the onset of study treatment. A listing will present abnormal hematology values (except for lymphocytes between 200 cells/uL and the lower limit of normal) for all patients.

Patients with abnormalities in hematology assessments, defined as absolute lymphocyte count (ALC) < 200 cells/uL, absolute neutrophil count (ANC) < 500 cells/uL, ANC < 1000 cells/uL, and total WBC > 20,000 cells/uL will be summarized by treatment group.

Actual value, change, and percent change in ALC will plotted in line graphs over time showing the means and standard errors (SE).

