#### 10.2.2. Blood Chemistry

The following laboratory tests will be included for blood chemistry summary tables at the screening visit: sodium, potassium, chloride, calcium, magnesium, phosphate, blood urea nitrogen, random glucose, hemoglobin A1c, albumin, alkaline phosphatase, creatinine, SGPT/ALT, SGOT/AST, gamma glutamyltransferase (GGT), amylase, total bilirubin, conjugated bilirubin, total cholesterol, triglycerides, HDL and LDL. For all other visits, which will be subject to change from Baseline reporting, the tests will include blood urea nitrogen, hemoglobin A1c, albumin, alkaline phosphatase, creatinine, SGPT/ALT, SGOT/AST, GGT, amylase, total bilirubin, and conjugated bilirubin.

A listing will present abnormal chemistry values for all patients.

The incidence of patients with abnormalities in Liver Function Tests (SGPT/ALT, SGOT/AST, and GGT) will be summarized overall and at each visit for each treatment group for the following categories:

- > 1 x upper limit of normal (ULN)
- $> 2 \times ULN$
- $> 3 \times ULN$
- $\geq 4 \times ULN$
- $\geq 5 \times ULN$

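### SAP 10.5 plans no by-arm count of large measured FEV1 or FVC falls, so symptom-free falls above 50% of predicted that the investigator does not judge clinically significant appear in no count table (minor)

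*SAP*

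**What the plan says.** SAP 10.5 states that for FEV1 and FVC "summary tables for actual value, change, percent change, percent predicted, change in percent predicted, and percent change in percent predicted will be produced". It adds: "Line plots of FEV 1 , FVC, and DLCO results over time will be presented". All pulmonary function results are also listed. Under SAP 5, a continuous summary consists of n, mean, SD, median, minimum and maximum.

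Both documents treat pulmonary decline as a named risk. SAP 10.1.7 includes among the adverse events of special interest "pulmonary function (decline in FEV1, FVC, and DLCO measurements", and Protocol 9.1.2.5 does the same. Protocol 12.4 gives the drug-class background: "An initial sharp decrease followed by a slow progressive decline over time in FEV 1 was observed in fingolimod clinical studies".

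Elsewhere the SAP counts patients past a limit:
- Haematology (SAP 10.2.1): "Patients with abnormalities in hematology assessments, defined as absolute lymphocyte count (ALC) < 200 cells/uL", with further limits for neutrophils and total white cells.
- Liver tests (SAP 10.2.2): "The incidence of patients with abnormalities in Liver Function Tests (SGPT/ALT, SGOT/AST, and GGT) will be summarized overall and at each visit", in five bands of the upper limit of normal.
- Vital signs (SAP 10.3): "The number and percentage of patients with clinically relevant abnormalities will be presented by treatment group", plus minimum heart rate on Day 1 in seven bands.

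The only numeric on-treatment limit for FEV1 or FVC is below 50% of predicted, which leads to discontinuation of study drug (Protocol 9.4.4.1 and 12.4).

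**The concern.** Means, line plots and a minimum show that something changed in an arm and how low the single worst patient went. They do not show how many patients fell. If a small subset loses a large share of lung function while the rest stay stable, the arm mean barely moves.

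The adverse event tables in SAP 10.1.5 and 10.1.7 count reported events, not measured values. Above 50% of predicted, Protocol 12.4 requires abnormal tests to be followed up but sets no numeric trigger for an adverse event. Reporting then depends on symptoms, clinical significance, therapy or discontinuation (Protocol 12.5 and 12.7, SAP 10.1).

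A reader comparing the arms on this named risk would have to count from the listing, for about 1200 patients at up to four scheduled visits, with a cut-off picked after unblinding. Efficacy, alpha and data collection are not affected.

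**Working it through.** The plan gives no figure to reproduce, because the point is a table that is not there. The check has three steps.

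**1. Which falls does a planned table count?**
- Below 50% of predicted: a protocol-defined event of special interest that leads to discontinuation. It should largely surface under SAP 10.1.5 and 10.1.7.
- Above 50%, with symptoms, therapy or a judgement of clinical significance: an adverse event under Protocol 12.5 and 12.7, so tabulated.
- Above 50%, with none of these: in the continuous summaries and the listing only. No planned table counts these patients.

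**2. How wide is that last range?** Inputs: FEV1 or FVC below 70% of predicted at screening is excluded (Protocol 9.4.2, criterion 38); the discontinuation limit is 50% (Protocol 9.4.4.1). Taking the predicted value as constant, the fall from baseline needed to reach 50% is 1 − 50/entry:
- entry 70%: 28.6%
- entry 80%: 37.5%
- entry 90%: 44.4%
- entry 100%: 50.0%

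Protocol 7.2.4 reports falls of more than 20% in FVC and FEV1 in two Phase 1 subjects. A 20% fall leaves 70 × 0.8 = 56% or 100 × 0.8 = 80% of predicted. A fall of that size does not bring any patient who meets the entry criterion to the 50% limit.

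**3. Would the planned summaries show it?** This is an illustration on assumed inputs, none of which the documents give except the arm size of about 400 (SAP 5.1). For one measure, percent change from baseline is taken as normal with mean 0 and SD 5 or 10, and 0, 8 or 20 patients are shifted down by 25 points.
- Shift in arm mean = 25 × k/400, for k shifted patients.
- Arm SD = √(SD² + 625p(1 − p)), with p = k/400.
- P(fall > 20), unaffected patient = Φ(−20/SD): 0.00003 at SD 5, 0.0228 at SD 10.
- P(fall > 20), shifted patient = Φ(5/SD): 0.841 at SD 5, 0.691 at SD 10.
- Expected count at one visit = (400 − k) × P(unaffected) + k × P(shifted).

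| Shifted patients | Mean moves by | Arm SD (SD 5 / SD 10) | Expected count (SD 5 / SD 10) |
|---|---|---|---|
| 0 | 0 | 5.0 / 10.0 | 0.01 / 9.1 |
| 8 | 0.5 | 6.1 / 10.6 | 6.7 / 14.4 |
| 20 | 1.25 | 7.4 / 11.4 | 16.8 / 22.5 |

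At SD 5 the count separates the arms clearly. At SD 10, against an unaffected arm, 8 shifted patients give a difference of 14.4 − 9.1 = 5.3, with a Poisson SE of √(14.4 + 9.1) = 4.8. Twenty shifted patients give 22.5 − 9.1 = 13.4, with an SE of √(22.5 + 9.1) = 5.6.

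Taking the worst of four visits adds noise. With no affected patients, simulation with equal correlation between visits gives an expected 0.01 to 0.1 patients per arm past the cut-off at SD 5. At SD 10 it gives 35.2, 28.6, 21.0 and 9.1 for correlations of 0, 0.5, 0.8 and 1.

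**The case against.** The strongest case against has five parts.

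**No commitment is broken.** The statistical methods in the protocol synopsis promise incidence or outlier tables for vital signs and ECG, and shift tables in a laboratory context. They promise no threshold count for pulmonary function. This stands. A reader might infer that the SAP contradicts the protocol or that lung function is its one exception. Neither holds: ECG in SAP 10.4 also has no numeric cut-off counts, only an overall interpretation.

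**The uncounted group is narrow.** A reader might infer that large falls in lung function in general would go uncounted. The documents do not support that. Symptoms, therapy or clinical significance make an abnormal result an adverse event, every abnormal pulmonary test must be followed up, and values below 50% of predicted stop treatment. This stands and sets the scope of the point.

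**The Phase 1 example points the other way.** Both subjects with falls above 20% were on 2 mg, twice the top dose here, and both falls were reported as Grade 1 adverse events. So the example does not show that falls of this size go unreported. It only supplies a size to count.

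**Nothing is lost.** All results are listed, the minimum shows the worst patient, and the count can be produced later. Table shells, which the protocol promises, are not among the supplied documents and cannot be checked. This stands, but a count made later would use a cut-off chosen with the data in view.

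**The count is noisy and the illustration is assumed.** Also true. At SD 10, 8 affected patients cannot be told from chance. That limits what the table can show; it does not remove the use of having it.

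**Conclusion.** The point holds as a minor, cheap improvement. No planned table counts patients whose FEV1 or FVC falls substantially but stays above 50% of predicted, without symptoms and without being judged clinically significant. The range is wide: 28.6% to 50.0% of baseline can be lost before the limit is reached, for entry values of 70% to 100% of predicted. That part rests on document figures, plus a predicted value taken as constant.

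The claim that arm means hide such patients rests on assumed inputs. Twenty of 400 patients losing 25 points moves the mean by 1.25 points, although at SD 5 the arm SD would also rise visibly, from 5.0 to 7.4. The documents give no evidence of how many patients would fall into the uncounted group.

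**What to change.** In SAP 10.5, add one descriptive table of the number and percentage of patients, by arm, with a fall of more than 20% from baseline in FEV1 or in FVC. Show it by visit (Months 3, 6, 12 and 24, as scheduled in Protocol Table 3) and for the worst post-baseline value, including the early termination visit.

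Use as denominator the patients with a baseline value and a post-baseline value in that period. This must be stated, because the SAP 5 default is all patients in the arm and SAP 10 does not impute missing safety data. Read the counts against the interferon arm, without a test. A row for values below 50% of predicted is optional, since those should largely appear in the adverse event and discontinuation tables.

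The cost is one table from variables that SAP 10.5 already derives. The downside is that the 20% cut-off is a choice, anchored only to two Phase 1 subjects on 2 mg, and the count includes measurement noise, most of all in the worst-value row.

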### 10.6. Physical Examination

Physical examination results will be listed.

## 10.7. Chest X-ray

Chest x-ray will be performed at screening for patients with a positive inconclusive result of QuantiFERON Gold test or other interferon gamma release assay. The results will be listed

## 10.8. Suicidality

Suicidality assessment from a self-administered C-SSRS (Posner, 2011) system will be summarized for each treatment group.

## 10.9. Other Assessments

A summary table of dermatological abnormalities by visit will be presented. Listings of dermatological abnormalities and abnormalities in optical coherence tomography (OCT) assessment will be provided.

### 11. INTERIM ANALYSIS

No interim analyses are planned for this study

# APPENDIX A IMPUTATION ALGORITHM FOR PARTIAL AND MISSING DATES

Incomplete Dates of MS Symptom and MS Diagnosis

If day is missing, day will be set to 15th of the month.

If month is missing, month and day will be set to July 1st.

If either imputation above results in a date  $\geq$  informed consent, then impute it as the date of informed consent -1.

#### Adverse Event

If AE resolution date is present and after first dose date:

Year of onset	Month of onset	Day of onset	Onset date to be imputed as
Missing	Missing	Missing	Date of first dose
year = year of first dose	Missing	Non-missing	Set month to month of first dose
year = year of first dose	Missing	Missing	Set month and day to those of first dose
year < year of first dose	Missing	Non-missing	set month to December
year < year of first dose	Missing	Missing	set month and day to December 31
year > year of first dose	Missing	Non-missing	set month to January
year > year of first dose	Missing	Missing	set month and day to January 1
year = year of first dose	Month = month of first dose	Missing	Set day as day of 1st dose
year = year of first dose	Month < month of first dose	Missing	Set day as last day of onset month
year = year of first dose	Month > month of first dose	Missing	Set day as first day of onset month
year < year of first dose	Non-missing	Missing	Set day as last day of onset month
year > year of first dose	Non-missing	Missing	Set day as first day of onset month

If AE resolution date is present and prior to first dose date, no need to impute incomplete AE start date. The AE is not treatment emergent.

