Efficacy and Safety of Oral RPC1063 in RMS Patients

#### Footnotes to Table 3

- 1 At Visit 1 an interim medical history will be performed to complete the screening medical history. Medical events that occur between screening and first dose will be recorded as medical history. All SAEs must be reported from the time of signing the informed consent; AEs are collected after the first dose.
- 2 Laboratory tests include Hematology, Chemistry, and Urinalysis.
- 3 Serum beta-hCG at screening, urine beta-hCG at each visit. If the urine pregnancy test is positive, do not dose and confirm with a serum pregnancy test.
- 4 Serology testing will be performed at screening to determine the patient's immune status with respect to the following viruses: Human immunodeficiency virus (HIV) antibodies, anti-hepatitis A virus IgM, hepatitis B surface antigen (HBsAg) and anti-hepatitis B core antigen (HBcAg) IgM, anti-hepatitis C virus (HCV) IgG or IgM. In addition, patients must have documentation of positive Varicella Zoster Virus (VZV) IgG antibody status or complete VZV vaccination at least 30 days prior to first dose of study medication.
- 5 The TB screening test (purified protein derivative) should be performed during the screening period and all testing must be completed prior to administration of study drug on Day 1 As available locally, an interferon gamma release assay such as QuantiFERON Gold test may be used as an alternative screening TB test or as a confirmatory test to rule out a false positive result using purified protein derivative.
- 6 Height at screening only.
- 7 A chest X-ray is not required if performed within 60 days prior to randomization and if documentation is on file.
- 8 Refer to Table 5 for details of cardiac monitoring.
- 9 RPC1063 (0.5 or 1 mg) will be administered daily for the study duration; IFN β-1a 30 μg will be administered by IM injection weekly.
- 10 Brain MRI scans will include a T2 and T1 scan (with and without Gadolinium) and will be performed at screening and then yearly.
- 11 Three MSFC practice assessments must be performed before baseline. These may be performed at the screening visit, or at any time between the screening and baseline visit.

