#### 10.1. Adverse Events

A treatment emergent AE is any reaction, side effect, or other untoward event, regardless of relationship to study drug, which occurs any time after the first dosing of study drug, until 28 days following the last dose of study drug. During the study, clinically significant adverse changes in clinical status, ECGs, and physical examinations are considered AEs. Any patient complaints associated with such an abnormal finding will also be reported as an AE.

Adverse events include, but are not limited to: (1) a worsening or change in nature, severity, or frequency of conditions present at the start of the study; (2) patient deterioration due to primary illness; (3) intercurrent illness; and (4) drug interaction.

An abnormal laboratory value will only be reported as an AE if it involves therapeutic medical intervention, if the Investigator considers it to be an AE, or if it leads to study discontinuation.

A treatment-emergent AE is defined as an AE that meets any of the following conditions:

- Begins on or after Study Day 1
- Begins before Study Day 1 and worsens in severity on or after Study Day 1.

Adverse events with unknown onset dates or unknown end dates will be counted as having occurred during the study treatment period unless the event resolves before Study Day 1. Adverse events with unknown severity will be counted as severe. Adverse events with unknown relationship to study drug will be counted as probably related to study drug.

Only treatment-emergent AEs will be presented, according to the Medical Dictionary for Regulatory Activities (MedDRA®), system organ class (SOC), and preferred term (PT).

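### One row of the SAP's partial-date rule can give an adverse event that resolved after first dose an onset before first dose, or on a date that does not exist

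*SAP*

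**What the plan says.** SAP 5.4.4 (Missing and Partial Data) sends partial dates to Appendix A. The adverse event table there is introduced by "If AE resolution date is present and after first dose date", so it covers only events that were still present after dosing began. It has 12 rows. The row at issue has onset year equal to the year of first dose, month missing and day recorded; its instruction is "Set month to month of first dose".

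The nearby rows read differently:
- First-dose year, month and day both missing: "Set month and day to those of first dose".
- First-dose year, onset in the month of first dose, day missing: "Set day as day of 1st dose".
- Later year, month missing, day recorded: "set month to January", which is always after first dose.

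SAP 10.1 defines an event as treatment-emergent if it starts on or after Study Day 1, or if it starts earlier and then worsens on treatment. It also says "Adverse events with unknown onset dates or unknown end dates will be counted as having occurred during the study treatment period", except where the event resolved before Study Day 1. On reporting it says "Only treatment-emergent AEs will be presented", while SAP 10.1.1 puts all adverse events in a listing.

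For Part B, footnote 1 to Protocol Table 3 says "AEs are collected after the first dose"; serious events are reported from consent.

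**The concern.** The row fills in the month and leaves the recorded day alone. If that day is earlier in the month than the day of first dose, the imputed onset falls before Study Day 1. A program that follows SAP 5.4.4 to Appendix A, and then applies the definition in 10.1, would drop the event from the treatment-emergent summaries unless it worsened.

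The error can only remove events from those summaries. That runs against the cautious direction of 10.1, which counts unknown severity as severe and unknown relationship as probable. It also means that a record with more information (a known day) can be excluded, while the same record without the day is always counted.

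For the MS symptom and diagnosis dates, the same appendix does check the imputed date against a bound: a date on or after consent is reset to the day before consent. The adverse event rules have no such check.

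**Working it through.** The plan states no figure on this point, so there is none to reproduce. The example dates below are constructed.

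**1. The rule applied to one record.** First dose 20 March 2014; onset day 5, month unknown, year 2014; resolved 12 June 2014.
- Imputed onset: 5 March 2014, which is before 20 March.
- Possible true onsets up to resolution: the 5th of January, February, March, April, May or June.
- For a non-serious event recorded as the protocol directs, only April, May and June remain. The rule picks a date that the collection rule excludes.

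**2. The same event with less information.** If the day were missing too, the onset would be set to 20 March. If the month were known to be March and the day missing, it would again be 20 March. Both versions are treatment-emergent.

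**3. Invalid dates.** With first dose in April and recorded day 31, the rule gives 31 April. The other rows that fill in only a month use January or December, which have 31 days, so they cannot do this.

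**4. Share of records in this row dated before first dose.** This happens when the recorded onset day is smaller than the first-dose day *d*. The documents give no distribution for either day, so the following are assumptions.

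(a) Both days independent and uniform over a 30-day month: the mean of (*d* − 1)/30 is (0 + 1 + … + 29)/(30 × 30) = 435/900 = 0.483. On a real 365-day calendar it is 48.4%.

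(b) Onset on or after first dose and in the same calendar year, first dose uniform over the year, every pair of dates enumerated:

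| Onset after first dose | Dated before first dose |
|---|---|
| Uniform to 31 December | 43.8% |
| Exponential, mean 180 days | 43.5% |
| Exponential, mean 90 days | 42.7% |
| Exponential, mean 60 days | 41.6% |
| Exponential, mean 30 days | 37.8% |
| Exponential, mean 14 days | 29.6% |

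The share varies strongly with the first-dose date. With an independent onset day it is 0% for a first dose on day 1 of the month, 46% for day 15 and 89% for day 28. With uniform later onset it is 47% for a January first dose, 31% for November and 0% for December.

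If the later of the imputed date and the first-dose date is taken, the share is 0% in every case.

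**5. Consequence for the tables.** Two readings are possible.
- *Appendix A governs:* the imputed date fails the first treatment-emergent condition, and the event is left out unless it worsened. The loss is the share in step 4.
- *The unknown-onset rule in 10.1 governs:* every event in this block resolved after first dose, so every one counts as on treatment. The loss is 0%.

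The SAP does not say whether an unknown onset date includes a partial one, or which provision takes precedence.

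**The case against.** The best defence is the unknown-onset rule in 10.1. If it covers partial dates, it keeps every event in this row, including the example above, and nothing is lost. That reading is reasonable, but the text does not secure it: SAP 5.4.4 routes partial dates to Appendix A, and Appendix A itself rules on treatment-emergence for events that resolved before first dose. The defence turns a certain loss into an unresolved conflict; it does not remove the conflict.

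A reader might infer that about half of all events with an unknown onset month vanish from every adverse event table. The documents do not support that, for four reasons:
- Only one row of 12 is affected. If the day is also missing, the first-dose date is used.
- The 48% treats the two days as independent. Once onset must follow first dose, as the collection rule implies for non-serious events, the range is about 30% to 44%.
- An event that worsened on treatment still qualifies.
- All adverse events are listed (SAP 10.1.1), serious events are listed separately (10.1.4), and events of special interest are listed (10.1.7).

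It is also fair to say that such records should be rare. Protocol 12.1 has the investigator ask about events at every visit, Part B visits are about three months apart or closer, and SAP 1.1 plans ongoing edit checks. A serious event with a known day and unknown month is harder still to imagine, given entry within 24 hours of site awareness (Protocol 12.3). The rule is the same in all arms, and SAP 10 plans no hypothesis tests on safety.

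Finally, serious events are collected from consent, so a pre-dose onset can be real for them. A floor would move such an event onto treatment if its order is unclear. That is the direction 10.1 already chooses.

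**Conclusion.** The row is wrong as written, and the point is minor. It can assign a pre-dose or non-existent onset to an event that resolved after first dose. It disagrees with its neighbours and with the unknown-onset rule in 10.1, and no order of precedence is stated.

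Under the literal reading, about 30% to 48% of the records in this one row would be dated before first dose. The upper end assumes independent days; the lower end assumes onset concentrated soon after first dose (mean 14 days). These distributions are assumptions. The documents do not give the number of such records, and it is probably small.

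Nothing in the documents points to an imbalance between arms or a material change in the safety profile, and no efficacy analysis is touched.

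**What to change.** Make two additions to the SAP before database lock.

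1. In this row of Appendix A: if the imputed date precedes first dose or is not a valid date, set onset to the date of first dose.
2. In 10.1 or Appendix A: the unknown-onset rule of 10.1 decides treatment-emergent status for any partial date that leaves the order relative to first dose undetermined.

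The limit in the second sentence should apply to the floor as well. Where every possible date is before first dose (for example, first dose 20 December and recorded day 5 of the same year), the order is known, and the record should be queried instead of moved.

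The cost is a sentence or two of text and about one line of code. Data collection and trial conduct are unaffected.
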